5.1.1 Maximum-Tolerated Dose

The MTD will be selected from the dose levels using a 3+3 dose-escalation, if possible.

5.1.2 Intra-patient dose adjustment

Patients may be permitted an intra-patient dose-escalation of AC699 to a higher dose level that does not have any treatment-related AE of Grade 3 or higher and has been cleared and deemed safe by the SRC if they have completed Cycle 1 at their assigned dose level and continued on-study with no \geq Grade 2 treatment-related AEs. The Investigator must consult with the Medical Monitor to confirm if the patient is permitted be dose-escalated to a dose level already cleared by the SRC. The patient data will continue to be collected for evaluation of safety and clinical activity, and all assessments will continue according to the Schedule of Assessments.

5.1.3 Safety Review Committee

After each dose level during the dose-escalation, a Safety Review Committee (SRC) will evaluate the available data including, safety, tolerability, and PK data to decide the next dose level as per the 3+3 dose escalation design. The SRC has discretion to consider the MTD or other doses as the RP2D. However, the RP2D will be no greater than the MTD.

The SRC will consist of:

- Coordinating Investigator, who will chair the committee, or delegate
- Principal Investigator or delegate from the Investigational sites

CONFIDENTIAL

Study Drug: AC699 Sponsor/Development Innovations Study Numbers: AC699-001/BRE 401

- Medical Monitor(s) for the study or delegate
- Sponsor representative (Safety Physician, Clinical Lead, or delegate(s)).

The Study Pharmacologist, Study Statistician, Patient Safety Scientist, Project Manager and other experts may also be invited as appropriate.

Further internal or external experts may be consulted by the SRC as necessary. The Sponsor representative (Safety Physician, Clinical Lead, Medical Monitors, or delegates) should always be present at the SRC if there are safety issues for discussion. The SRC will be consulted throughout the study on issues related to study safety.

Once there are evaluable patients at a dose level, the SRC will review and assess all available safety data and any other relevant data from the cohort to make a decision on how the study should proceed. Any dose interruptions and reductions will be taken into account. When available, emerging PK data will be evaluated to inform the dose-escalation or dosing regimen decisions on at least a prior dose level lagging basis.

The decision may be to:

- Proceed with dose-escalation
- Decide what the next dose level should be
- Expand the existing cohort
- De-escalate the dose to a previous lower dose level or to an intermediate lower dose level
- Stop the dose-escalation part of the study

Any patient started on treatment in error, as he/she failed to comply with all of the eligibility criteria but meets the criteria of an evaluable patient, will be reviewed on a case by case basis by the SRC to determine if the patient should be included or excluded in the evaluation of the next dose level.

The decisions and decision-making of the SRC on the next dose level will be documented and provided to the Investigators prior to dosing any new patients.

The timing, frequency, or need for safety evaluations may be revised, in consultation with the SRC, in response to emerging data.

5.2 End of Study Treatment (EOT)

Patients will be discontinued from study treatment for any of the following reasons:

- Objective disease progression (Patients who are receiving clinical benefit in the opinion of the treating Investigator may be allowed to stay on study treatment after consultation with the Medical Monitor and Sponsor Representative)
- Intolerable toxicity that are irreversible thought to be related to study drug
- Treatment discontinuation criteria as per Dose Modification criteria (See Section 6)
- Conditions requiring therapeutic intervention not permitted by the protocol
- Intercurrent illness interfering with the patient's ability to follow study requirements (treatment or assessments); this will be at the Investigator's discretion

CONFIDENTIAL

Study Drug: AC699 Sponsor/Development Innovations Study Numbers: AC699-001/BRE 401

- Another condition leading to patient's inability to comply with study requirements
- Patient lost to follow-up
- Patient withdraws consent from study treatment or study participation altogether
- Start of a new anti-cancer therapy
- Patient's death
- Patient's participation in the study is terminated by Investigator
- Study termination

After discontinuation from protocol treatment, patients must be followed for AEs for 30 days after their last dose of study drug. Patients discontinuing study treatment prior to disease progression (per RECIST v1.1) will go on to extended follow-up. During extended follow-up response assessments will be performed as described in Section 7.4.3. All new AEs occurring during the 30-days following termination of treatment must be reported and followed until resolution or stabilization unless, in the opinion of the Investigator, these values are not likely to improve because of the underlying disease. In this case, the Investigator must record his or her reasoning for this decision in the patient's medical records and indicate that the outcome is not resolved on the AE pages of the electronic case report form (eCRF).

All patients who have Grade 3 or 4 laboratory abnormalities (per National Cancer Institute Common Terminology Criteria for Adverse Events [NCI CTCAE; CTCAE Version 5.0] at the time of discontinuation must be followed until the laboratory values have returned to Grade 1 or 2 unless it is, in the opinion of the Investigator, not likely that these values are to improve and/or are the results of underlying diseases. In this case, the Investigator must record his or her reasoning for making this decision in the patient's medical records and indicate on the AE pages that the outcome is not resolved on the eCRF.

5.3 Study Duration and End of Study (EoS)

The **start of the study** is defined as the date when the first patient in the whole study signs informed consent.

The **end of the study** is defined as the date of the last visit (including all follow-up visits) of the last patient in the whole study.

Patients will continue on treatment until disease progression as defined in Section 9 or other criteria for treatment discontinuation are met. Patients will continue in the study until any one of the criteria occurs:

- Start of a new anti-cancer therapy
- Intercurrent illness interfering with the patient's ability to follow study requirements (treatment or assessments); this will be at the Investigator's discretion
- Another condition leading to patient's inability to comply with study requirements
- Patient withdraws consent from study participation
- Patient's participation in the study is terminated by Investigator
- Patient is lost to follow-up

CONFIDENTIAL

Sponsor/Development Innovations Study Numbers: AC699-001/BRE 401

Final Protocol: 07 May 2024 Version 4.0

- Patient's death
- End of the whole study.

5.4 Concomitant Medications

Patients will be asked about prior medications during screening and instructed not to take any additional medications during the course of the study without prior consultation with the study team. At each visit, the patient will be asked about any new medications he or she is taking or has taken after the start of the study drug.

5.4.1 Permitted Concomitant Medications and Therapy

Supportive care per institutional standard such as anti-emetics is allowed during the study.

Medications may be administered for maintenance of existing conditions prior to study enrollment or for a new condition that develops while on study, including but not limited to the following:

- Bisphosphonate use, as recommended according to practice guidelines.
- Receptor activator of nuclear factor kappa-B ligand (RANKL) inhibitor use, as recommended according to practice guidelines.
- Growth factors and blood transfusions will be permitted after Cycle 1.
- Palliative radiotherapy is permitted.

CYP inhibiting and CYP inducing agents are allowed in the study. Nonetheless, since this is a first-in-human clinical trial, patients who are using these agents while on study drug should be closely monitored.

Medicinal products that alter the pH of the upper GI tract may alter the solubility of AC699, expected to impact and limit its bioavailability. Such agents include, but are not limited to, proton pump inhibitors (e.g., omeprazole), H2-antagonists (e.g., ranitidine) and antacids. Proton pump inhibitors are prohibited (see Section 5.4.2). For patients who require mandatory use of antacid medication, proton pump inhibitors must be replaced with H2-antagonists or antacids. If H2 antagonist or antacid is used, study drug should be taken \geq 2 hours before or 10 hours after dosing with H2-antagonists. Antacids, locally-acting acid neutralizing agents intake, are to be separated from study drug doses by 2 hours.

Supportive care and other medications considered necessary for the patient's safety and well-being may be given at the discretion of the Investigator, with the exception of those listed under section "Prohibited Concomitant Medication" (Section 5.4.2).

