5.4.2 Prohibited Concomitant Medications

The following treatments are prohibited while in this study:

• No other investigational therapy should be given to patients. No anticancer agents other than the study treatments should be given to patients. If such agents are required for a patient, then the patient must first be withdrawn from the study.

CONFIDENTIAL

Sponsor/Development Innovations Study Numbers: AC699-001/BRE 401

Final Protocol: 07 May 2024 Version 4.0

- Anticoagulation with coumarin-derivatives is not permitted. However, the use of anticoagulants to keep the port line patent will be permitted. Should a thrombotic event occur while the patient is in the study and receives anticoagulant treatment, and the patient remains in the study, oral Xa inhibitors will be the preferred anticoagulant treatment.
- Proton pump inhibitors are prohibited due to their long PD effect. This type of drugs should be replaced with H2-antagonists or antacids.
- Any new or concomitant QT prolonging medications within the last 6 months.

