Appendix B: Response Evaluation Criteria in Solid Tumors (RECIST) Version 1.1

Introduction

This appendix details the general implementation of RECIST v1.1 (Response Evaluation Criteria in Solid Tumors version 1.1) (Eisenhauer et al. 2009) guidelines for the study with regards to Investigator assessment of tumor burden.

Definition of Measurable and Non-measurable Lesions

Patients with at least one tumor lesion or malignant lymph node (either measurable and/or non-measurable) that can be accurately assessed at baseline can be included in the study. At baseline, tumor lesions/lymph nodes will be categorized as measurable or non-measurable as follows:

Measurable:

Tumor lesions: To be considered measurable disease, tumor lesions must be accurately measured in at least one dimension (longest diameter in the plane of measurement is to be recorded) with a minimum size of:

10 mm by computed tomography (CT scan slice thickness/interval no greater than 5 mm)

10 mm caliper measurement by clinical exam (lesions which cannot be accurately measured with calipers should be recorded as non-measurable)

20 mm by chest X-ray

Malignant lymph nodes: To be considered pathologically enlarged and measurable, a lymph node must be ≥ 15 mm in short axis when assessed by CT scan (CT scan slice thickness recommended to be no greater than 5 mm). At baseline and in follow-up, only the short axis will be measured and followed.

Non-measurable:

All other lesions, including small lesions (longest diameter <10 mm or pathological lymph nodes with \ge 10 to <15 mm short axis at baseline).

Truly non-measurable lesions include the following: leptomeningeal disease, ascites, pleural/pericardial effusion, inflammatory breast disease, lymphangitic involvement of skin or lung, and abdominal masses/abdominal organomegaly identified by physical examination that is not measurable by CT or MRI.

Previously irradiated lesions or lesions subjected to other local-regional therapy. **Note:** These lesions may be considered measurable disease if there has been demonstrated progression.

Special Consideration Regarding Lesion Measurability:

Bone lesions

Study Drug: AC699

Bone scan, PET scan, or plain films are not considered adequate imaging techniques to measure bone lesions. However, these techniques can be used to confirm the presence or disappearance of bone lesions.

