Clinical lesions: Clinical lesions will only be considered measurable when they are superficial and ≥ 10 mm diameter as assessed using calipers (e.g., skin nodules). For the case of skin lesions, documentation by color photography including a ruler to estimate the size of the lesion is suggested.

X-ray: Chest CT is preferred over chest X-ray, particularly when progression is an important endpoint, since CT is more sensitive than X-ray, particularly in identifying new lesions. However, lesions on chest X-ray may be considered measurable if they are clearly defined and surrounded by aerated lung.

Ultrasound: Ultrasound is not useful in assessment of lesion size and should not be used as a method of measurement. Ultrasound examination can, however, be used to identify the presence of new lesions. If new lesions are identified by ultrasound in the course of the study, confirmation by CT or MRI is advised.

Endoscopy, Laparoscopy, Tumor markers, Cytology, Histology: The utilization of these techniques alone will not be used for objective tumor response measurements.

FDG-PET: FDG-PET scans may be used as a method for identifying new lesions in the assessment of progression, according with the following algorithm: New lesions will be recorded where there is positive FDG uptake (defined as when an uptake greater than twice that of the surrounding tissue is observed) not present on baseline FDG-PET scan or in a location corresponding to a new lesion by CT/MRI at the same visit. If there is no baseline FDG-PET scan available, and no evidence of new lesions by CT/MRI then follow-up CT/MRI assessments should be continued, scheduled as per protocol or clinically indicated, in order to confirm new lesions.

Tumor response evaluation

This section provides the definitions of the criteria used to determine objective tumor response. *Evaluation of target lesions:*

CONFIDENTIAL

Sponsor/Development Innovations Study Numbers: AC699-001/BRE 401

Final Protocol: 07 May 2024 Version 4.0

Complete Response (CR)	Disappearance of all target lesions since baseline. Any pathological lymph nodes must have a reduction in short axis to <10 mm.
Partial Response (PR)	At least a 30% decrease in the sum of the diameters of target lesions, taking as reference the baseline sum of diameters.
Stable Disease (SD)	Neither sufficient shrinkage to qualify for PR nor sufficient increase to qualify for PD. Note, for the purpose of this protocol, SD is defined by at least a 4-week interval.

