4.6 Subsequent Anticancer Therapy

Anticancer therapy initiated after patient's discontinuation from the study treatment will be summarized by frequency and percentage of participants.

- Participants who received subsequent systemic therapy(ies)
- Participants who received subsequent procedure(s)
- Participants who received subsequent radiation

All subsequent anticancer therapies will be listed.

5 Efficacy Analysis

All efficacy data will be presented in listings. Tables and figures will be presented as applicable. All efficacy analyses will be performed using the EFF as a whole and subdivided by ESR1 mutational status.

The secondary endpoints are ORR, CBR, DoR, DCR, PFS.

The exploratory endpoints are as follows:

- 1. Change of $ER\alpha$ expression in tumors from baseline to post-treatment in paired biopsies.
- 2. Correlation between circulating tumor cell count at baseline and post-treatment and anti-tumor activity (ORR, CBR, DOR, DCR, and PFS)
- 3. Correlation between estrogen receptor gene 1 mutational status and anti-tumor activity (ORR, CBR, DOR, DCR, PFS).
- 4. Correlation between circulating tumor DNA levels at baseline and post-treatment and anti-tumor activity (ORR, CBR, DOR, DCR, PFS).

5.1 **Endpoint Foundations**

5.1.1 **Objective Tumor Response**

Tumor response will be evaluated using RECIST 1.1 criteria (Eisenhauer, et al 2009), every 8 weeks (\pm 5 days) for the first year of treatment, and then once every 16 weeks (\pm 5 days) thereafter or until disease progression (as determined by the investigator).

The response categories are as follows:

- Complete response (CR)
- Partial response (PR)
- Stable disease (SD)
- Progressive disease (PD)

Not Evaluable (NE)

The overall response to each assessment will be determined by the Investigator.

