5.1.2 Time-to-Event Variables

Time-to-event variables are defined as:

Time-to-Event (months) = (End Date - Start Date + 1) / 30.4375

 $DOR = (Earliest\ Date\ of\ Progression\ or\ Death-Date\ of\ First\ Documented\ CR\ of\ PR + 1)/30.4375.$

Start Dates

For all time to event variables other than DoR, the date of first dose of AC699 will be used as the start date.

The start date for DoR will be the date of first PR or CR, which has been subsequently confirmed.

End Dates

For DoR and PFS, the following rules will be used to derive the end dates for these endpoints:

- Events always take precedence to Censoring
- If multiple event dates are applicable, the earliest date will be used.
- If multiple censoring dates are applicable, the latest date will be used.

Table 2 shows data sources that can be used to determine end dates.

Table 2: Data Sources for End Dates

Date	Data Source	
Date of Death	Death CRF	
Date of Progression	Using RECIST 1.1 criteria, the earliest of the dates from the components that triggered the overall PD response from the Target Lesions, Non-target Lesions and New Lesions CRFs.	
Date of Last Evaluable Tumor Assessment	The latest data from the Target Lesions, Non-Target Lesions, and New Lesions CRFs reflecting the overall response, where the overall response is evaluable (i.e., not missing or NE), prior to further subsequent anticancer therapy if initiated.	
Date of Subsequent Anticancer Therapy	The earliest date is from the Subsequent Systemic Therapy, Subsequent Radiation, and Subsequent procedure CRFs.	

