5.1.3 Participant Follow-up

Participants are expected to be followed from the date of first dose of AC699 until the end of the study or death, whichever occurs first. Participants who discontinue the study treatment will continue to be followed up for disease progression (after the 30-day safety follow-up) through the end of the whole study as per the Protocol section 7.4.3: follow-up visits will be performed every 8 weeks (± 5 days) for the first year after treatment ends and then every 16 weeks (±5 days) thereafter until disease progression based on RECIST 1.1 or another withdrawal criterion is met:

- Start of a new anti-cancer therapy
- Lost to follow-up

Page 18 of 28

- Death
- Patient withdrawal
- End of the whole study

5.2 **Endpoints**

5.2.1 **Best Overall Response**

Best overall response (BOR) is defined as per RECIST 1.1 and will be calculated as the best response recorded from date of first dose of AC699 up until evidence of progression per RECIST 1.1.

The frequency and percentage of participants with each response will be summarized.

Confirmation of response is required (i.e., consecutive CRs, consecutive PRs or 1 CR and PR at least 4 weeks apart).

See Table 3 for scenarios of overall response.

Table 3: Best Overall Response with Confirmation of CR and PR Required

Overall Response			
Initial Subsequent		BEST Overall Response	
CR	CR	CR	
CR	PR	SD, PD, or PR*	
CR	SD	SD if minimum criteria for SD duration met, otherwise PD	
CR	PD	SD if minimum criteria for SD duration met, otherwise PD	
CR	Missing	SD if minimum criteria for SD duration met, otherwise NE	
PR	PR	PR	
PR	CR	PR	
PR	SD	SD	
PR	PD	SD if minimum criteria for SD duration met, otherwise PD	
PR	Missing	SD if minimum criteria for SD duration met, otherwise NE	

Abbreviations: CR = complete response, PR = partial response, SD = stable disease, PD = progressive disease, NE = not evaluable

When SD is believed to be the BOR, SD must have met the minimum interval of 7 weeks (8 weeks - 1 week for early assessments within window) since start of AC699. If it does not

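### Radiotherapy permitted during AC699 treatment has no cut-off in the SAP's response rules, so its effect can be counted as AC699 activity in ORR, CBR and DCR; for PFS and DOR its handling is unclear

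*Protocol*

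**What the plan says.** **Permission.** Protocol 5.4.1 states "Palliative radiotherapy is permitted", with no limit on site, timing or target status. The radiotherapy limits in exclusion criterion 1 concern treatment before the study. Protocol 5.4.2 bars other agents ("No anticancer agents other than the study treatments should be given to patients") and does not name radiotherapy. Protocol 5.2 lists "Start of a new anti-cancer therapy" as a reason to stop AC699.

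**Lesion rules.** Appendix B places "Previously irradiated lesions or lesions subjected to other local-regional therapy" among non-measurable lesions, unless progression has been shown, when lesions are classified at baseline. Its special cases for target lesions cover those that disappear, become too small, split, merge or grow too large, and nodes that shrink to normal size. Irradiation on study is not among them. Partial response is "At least a 30% decrease in the sum of the diameters of target lesions, taking as reference the baseline sum of diameters".

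**Response endpoints.** SAP 5.2.1 defines best overall response (BOR) as the "best response recorded from date of first dose of AC699 up until evidence of progression per RECIST 1.1". SAP 5.2.2 measures SD duration from the start of study drug to the last SD assessment.

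**PFS and DOR.** SAP Table 4 censors at the last evaluable assessment when further anticancer therapy is started. For the date of subsequent therapy, Table 2 says: "The earliest date is from the Subsequent Systemic Therapy, Subsequent Radiation, and Subsequent procedure CRFs". SAP 4.6 describes that category as follows: "Anticancer therapy initiated after patient's discontinuation from the study treatment will be summarized by frequency and percentage of participants". SAP 4.5 only lists concomitant procedures.

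**The concern.** ORR, CBR, DCR, DOR and PFS are all of the secondary endpoints for antitumour activity, and they are reported by dose level without a control group. If a lesion shrinks because it was irradiated, nothing in the response rules separates that from a drug effect. The error runs mainly one way: local treatment can create a response, prolong stable disease or hide growth elsewhere in the sum. Expanded dose levels hold about 20 patients (Protocol 10.2) or 15 (SAP 2.3), so a single case is visible in the rate, and these data are part of the totality that may suggest the RP2D.

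**Working it through.** The plan gives no figure to reproduce here. The check has three parts. Lesion sizes and responder counts are assumed for illustration.

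**1. Can an irradiated lesion alone produce a PR?**

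Let *w* be the lesion's share of the baseline sum and *s* its proportional shrinkage, with other target lesions unchanged. A PR requires *w* × *s* ≥ 0.30, that is *s* ≥ 0.30 / *w*.

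| Share of sum | Shrinkage needed for PR |
|---|---|
| 30% | 100% |
| 40% | 75% |
| 50% | 60% |
| 60% | 50% |
| 100% | 30% |

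Below a 30% share it cannot do so alone.

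Example A: targets of 40 and 30 mm.
- Baseline sum = 70 mm. Shrinkage needed in the 40 mm lesion = 0.30 × 70 / 40 = 52.5%.
- If it is irradiated and shrinks 55%: 40 × 0.45 = 18 mm. New sum = 18 + 30 = 48 mm.
- Change = (48 − 70) / 70 = −31.4%, a PR, with no change in the untreated lesion.
- Confirmation at least 4 weeks later does not remove a lasting radiotherapy effect.

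**2. Can it hide progression?**

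Example B: targets of 40, 20 and 20 mm.
- Baseline sum = 80 mm. The irradiated 40 mm lesion falls to 16 mm; the others grow to 26 mm each.
- Total = 68 mm; change = (68 − 80) / 80 = −15%, which is SD.
- Untreated lesions alone: 40 to 52 mm, +30% and +12 mm. Taken alone, they would meet the size rule for PD (at least 20% and 5 mm).

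**3. What is one misclassified responder worth?**

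| Patients per dose level | As counted (Clopper-Pearson 95% CI) | After reclassifying one | Difference |
|---|---|---|---|
| 20 | 4/20 = 20.0% (5.7 to 43.7) | 3/20 = 15.0% (3.2 to 37.9) | 1/20 = 5.0 points |
| 15 | 3/15 = 20.0% (4.3 to 48.1) | 2/15 = 13.3% (1.7 to 40.5) | 1/15 = 6.7 points |

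The same step applies to CBR and DCR.

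**PFS and DOR, by reading the sections together.** Radiation given after AC699 stops is caught by Tables 2 and 4. For radiation given during AC699:
- The Table 4 row is worded generally, which suggests it applies.
- Table 2 takes the date only from the subsequent-therapy forms, and SAP 4.6 describes that therapy as starting after discontinuation. This suggests it does not apply.
- Under Protocol 5.2 a new anti-cancer therapy ends treatment, while 5.4.1 allows radiotherapy during the study. Radiotherapy given on treatment is thus implicitly not a new anti-cancer therapy.
- SAP 5.1.2 gives events precedence over censoring, so a later PD or death could override the row in any case.

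Two analysts could handle the same patient differently and both cite the SAP.

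**The case against.** Several stronger readings are tempting, and the documents do not support them.

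- *A reader might infer that nothing in the SAP cuts PFS or DOR at radiotherapy.* That is wrong: Tables 2 and 4 censor at subsequent radiation. SAP 4.6 describes a summary table and is not a formal definition. What remains is an ambiguity about on-treatment radiotherapy.
- *A reader might infer that the plan orders an irradiated lesion to be kept in the sum.* It is silent. Appendix B has a not-evaluable category, and the investigator determines overall response. But nothing directs that category to be used for an irradiated lesion that is still measured, so the ordinary reading keeps it in.
- *A reader might infer that a patient whose only disease is a lytic bone lesion gains CBR and DCR credit once it is irradiated.* This is not established. With no target lesion and persisting non-target disease, Appendix B gives Non-CR/Non-PD, while CBR and DCR count CR, PR or sufficiently long SD. The SAP states no mapping between them.
- *A reader might assume a radiotherapy frequency and turn it into a bias in ORR.* No frequency is given, and not every irradiated patient changes category. A false PR needs a target lesion with a large enough share of the sum, enough shrinkage, and confirmation.

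It is also fair that this is a Phase I trial with a safety primary endpoint and no hypothesis testing, and that listings would allow a recorded procedure to be checked against a response. That lowers the stakes. It does not remove the gap, because a listing does not change how BOR, CBR or DCR is calculated.

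**Conclusion.** The gap is real for ORR, CBR and DCR. Applied as written, SAP 5.2.1 and 5.2.2 allow a radiotherapy effect on a target lesion to be credited to AC699. For PFS and DOR the point is narrower: the plan does not say clearly whether on-treatment radiotherapy triggers the existing censoring row.

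The size is 5.0 points (n = 20) to 6.7 points (n = 15) per misclassified patient in a dose level. The total effect is unknown because the frequency of on-study radiotherapy is not given. The conclusion assumes that an irradiated lesion continues to be measured and included, which follows from the absence of any contrary rule. The gap should be closed before the final analysis; it does not affect the primary safety objective.

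**What to change.** Leave the clinical permission unchanged and amend the analysis rules.

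1. **SAP 5.2.1 and 5.2.2.** Credit CR, PR and SD, and SD duration, only from assessments before on-treatment radiotherapy or other local therapy to a target or sole lesion. Let PD from non-irradiated or new lesions count at any time, including as BOR when there is no earlier qualifying response.
2. **SAP Table 4.** State whether on-treatment radiotherapy counts as further anticancer therapy, and reconcile Protocol 5.2 and 5.4.1 with SAP 4.6.
3. **PFS and DOR.** Keep the main analysis able to count later PD by treating post-radiotherapy scans as performed under the missed-assessment rule. Add a sensitivity analysis censored at the last evaluable scan before such radiotherapy. Take lesion site and date from the concomitant procedure or radiotherapy record.

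Simply rating every irradiated target lesion not evaluable is not a safe shortcut. Under Appendix B, later scans without PD would then be not evaluable overall. Table 2 excludes such scans, so the last evaluable date would freeze before radiotherapy. In the first 52 weeks, a true PD more than 18 weeks after that date would be censored.

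The cost is a paragraph or two in the SAP, a reconciling edit, and lesion site and date on the record. A few patients may lose a late response or some SD time.
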